## 4.0 Study population

A total of 15 adult participants with HCV genotype 1a infection, no prior HCV treatment experience and no evidence of cirrhosis will be enrolled including 10 patients with HCV genotype 1a only (no HIV coinfection) and 5 patients with HIV/HCV genotype 1a coinfection. HIV coinfecting patients will be required to be taking protocol specified antiretroviral therapy.

### 5.1 Inclusion/Exclusion criteria

#### Inclusion Criteria

Participants must meet all of the following inclusion criteria to be eligible for participation

1. Ability and willingness of participant to provide written informed consent.
2. Men and women age  $\geq 18$  to  $\leq 70$  years at study entry
3. Body mass index (BMI)  $\geq 18$  kg/m^2
4. HCV RNA  $\geq 10,000$  IU/mL at Screening
5. HCV genotype 1a at Screening or within 6 months of screening
6. Chronic HCV infection ( $\geq 6$  months) documented by prior medical history
7. HCV treatment-naïve with no prior treatment with any IFN, RBV, or approved or experimental HCV-specific DAA
8. Absence of cirrhosis as defined as transient elastography (FibroScan®) liver stiffness measurement  $< 12.5$  kPa within 6 months of screening
9. The following laboratory values obtained within 42 days prior to study entry.

- Hemoglobin > 10 g/dL for men and > 9 g/dL for women
- Platelet count  $\geq 90,000/\text{mm}^3$
- International normalized ratio (INR)  $\leq 1.5$
- Calculated creatinine clearance (CrCl)  $\geq 30$  mL/min
- Alanine aminotransferase (ALT) and aspartate aminotransferase level  $\leq 10$  x upper limit of the normal range (ULN)
- Total bilirubin <3 mg/dL
- Albumin  $\geq 3.5$  g/dL
- CD4+ cell count  $\geq 200$  cells/uL and CD4+ cell percentage  $\geq 14\%$  within 42 days of study entry at any US laboratory that has a Clinical Laboratory Improvement Amendments (CLIA) certification [HIV seropositive participants only]
- HIV RNA < 400 copies/mL prior to study entry by any US laboratory that has a CLIA certification or its equivalent [HIV seropositive participants only]

10. On a qualifying antiretroviral therapy (ART) regimen which is permitted with SOF/VEL. This allows for antiretroviral regimen that does not include Efavirenz, Nevirapine, or Tipranavir.

11. Women of childbearing potential must have a negative serum pregnancy test at Screening and a negative urine pregnancy test on Day 0 prior to liver biopsy

12. All participants must agree not to participate in a conception process (e.g., active attempt to become pregnant or to impregnate, sperm donation, in vitro fertilization).

13. If participating in sexual activity that could lead to pregnancy, the participant (men and women) must also agree to use two reliable methods of contraception simultaneously while receiving study treatment and for 30 days after stopping study treatment.

A combination of TWO of the following contraceptives MUST be used appropriately:

- Condoms (male or female) with or without a spermicidal agent
- Diaphragm or cervical cap with spermicide
- IUD (intrauterine device)

14. Participants who are not of reproductive potential (women who have been post-menopausal for at least 24 consecutive months or have undergone hysterectomy, bilateral tubal ligation, and/or bilateral oophorectomy or men who have documented azoospermia) are eligible without requiring the use of contraceptives. Acceptable documentation of sterilization and menopause is specified below.

Written or oral documentation communicated by clinician or clinician's staff of one of the following:

- Physician report/letter
- Laboratory report of azoospermia
- Follicle stimulating hormone-release factor (FSH) measurement elevated into the menopausal range as established by the reporting laboratory.

15. Participants must be able to adhere to dosing instructions for study drug administration and able to complete the study schedule of assessments, in the opinion of the investigator.

#### Exclusion Criteria

Subjects who meet any of the following exclusion criteria are not to be enrolled in this study:

1. Breastfeeding.
2. Known allergy/sensitivity or any hypersensitivity to components of study drugs or their formulation.
3. Acute or serious illness requiring systemic treatment and/or hospitalization within 42 days prior to study entry.
4. Active hepatitis B infection (positive HBsAg) within 42 days prior to study entry.
5. History of decompensated liver disease (including but not limited to encephalopathy, variceal bleeding, or ascites) prior to study entry.
6. Any cause of liver disease other than chronic HCV infection, including but not limited to the following:
  - Hemochromatosis
  - Alpha-1 antitrypsin deficiency
  - Wilson's disease
  - Autoimmune hepatitis
  - Alcoholic liver disease
  - Drug-related liver disease
7. Uncontrolled or active depression or other psychiatric disorder within 24 weeks prior to study entry that in the opinion of the investigator might preclude adherence to study requirements.
8. Active drug or alcohol use or dependence that, in the opinion of the investigator, would interfere with adherence to study requirements.

9. Serious illness including uncontrolled seizure disorders, active coronary artery disease within 24 weeks prior to study entry, or other chronic medical conditions that in the opinion of the investigator might preclude completion of the protocol.
10. Presence of active or acute AIDS-defining opportunistic infections within 12 weeks prior to study entry.
11. Active or history of malignancy within 2 years prior to study entry other than basal cell carcinoma of the skin and/or cutaneous Kaposi's sarcoma (KS) and/or cervical or anal dysplasia or carcinoma in situ.
13. Infection with any HCV genotype other than genotype 1a, or mixed genotype infection any time prior to study entry.
14. History of major organ transplantation with an existing functional graft any time prior to study entry.
15. History of acquired or hereditary bleeding disorder (e.g., hemophilia, warfarin use) or any other cause of or tendency toward excessive bleeding time prior to study entry.
16. Gastrointestinal disorder or post-operative condition that could interfere with the absorption of the study drug
17. Difficulty with blood collection and/or poor venous access for the purposes of phlebotomy
18. Planning to take any of the following medications or supplements from Day -7 to the end of treatment:
  - a. Proton pump inhibitors (patients may switch to H2 blockers up to Day -7)
  - b. Inducers of P-gp (including, but not limited to, dexamethasone, morphine, ritonavir, saquinavir, tipranavir)
  - c. Moderate to potent inducers of CYP2B6, CYP2C8, or CYP3A4 (including, but not limited to, efavirenz, etavirine, modafinil, rifampin, St. John's Wort, carbamazepine, phenytoin)
19. History of taking any dose of amiodarone within 6 months (180 days) of Day 0

## 6.0 Study treatment

### 6.1 Sofosbuvir/Velpatasvir/Voxilaprevir (SOF/VEL/VOX)

SOF/VEL/VOX is manufactured as a 400/100/100 mg tablet for oral administration once daily. Participants will take 1 tablet by mouth daily with food. This drug combination includes inhibitors of HCV non-structural proteins (NS) 5B (Sofosbuvir), 5A (Velpatasvir) and 3/4 (Voxilaprevir). Voxilaprevir and the combination of this agent with Sofosbuvir/Velpatasvir is approved by the FDA

and marketed in the United States under the trade name Vosevi ®. Additional information regarding this investigational product can be found in the Package Insert.

Participants may take H2-blockers only when they are taken  $\geq$  4 hours apart from dosing of SOF/VEL/VOX.

## **6.2 Sofosbuvir/Velpatasvir (SOF/VEL)**

SOF/VEL is manufactured as a 400/100 mg tablet for oral administration once daily. Participants will take 1 tablet by mouth daily without regard to food. This drug combination includes inhibitors of HCV non-structural proteins (NS) 5B (Sofosbuvir) and 5A (Velpatasvir) and is approved by the FDA and marketed in the United States under the name EPCLUSA®. Additional information regarding this commercial product can be found in the Package Insert.

[figure not shown]
Participants may take H2-blockers only when they are taken  $\geq$  4 hours apart from dosing of SOF/VEL.

## **7.0 Study design and Schedule of Events**

This study is an open-label, partially randomized clinical trial.

Table 2: Protocol Schema

All subjects will receive a total of 12 weeks of HCV treatment with oral direct acting antiviral (DAA) therapy. The study will occur in four steps.

Cohort 1: Paired liver biopsies on Day 0 and Day 7

Antiretroviral therapy (HIV seropositive only)													
Step 1	Step 2							Step 3			Step 4		
Screening/ Randomization	SOF/VEL/VOX or SOF/VEL							SOF/VEL			Follow-up		
	Entry/D0	D1	D2	D3	D4	D5	D6	D7	WK4	WK8	WK12	WK16	WK24
	Liver BX	VK	VK	VK	VK				Liver BX	VK	VK	VK	VK
VK								VK					

## Cohort 2: Paired liver biopsies on Day 0 and Day 4

Antiretroviral therapy (HIV seropositive only)													
Step 1	Step 2							Step 3			Step 4		
Screening/ Randomization	SOF/VEL/VOX or SOF/VEL							SOF/VEL			Follow-up		
	Entry/D0	D1	D2	D3	D4	D5	D6	D7	WK4	WK8	WK12	WK16	WK24
	Liver BX	VK	VK	VK	Liver BX			VK	VK	VK	VK	VK	VK
VK													

### 7.1 Step 1. Screening/ Randomization

Following informed written consent, participants will undergo screening procedures as per schedule of Events (Table 4).

The first nine subjects enrolled will be assigned to Cohort 1 as follows: 3 subjects in Arm A, 3 subjects in Arm B, and 3 subjects in Arm C. The subsequent six subjects will be enrolled into Cohort 2 as follows: 2 subjects in Arm A, 2 subjects in Arm B, and 2 subjects in Arm C.

Eligible participants who are coinfecting will be randomized before Entry/ Day 0. Randomization will occur for eligible monoinfected subjects with a 1:1 between SOF/VEL and SOF/VEL/VOX. Eligible subjects who are coinfecting will be non-randomly assigned to receive SOF/VEL. Subjects must enter Step 2 within 42 days of screening. Screening evaluations to determine eligibility must be completed within 42 days prior to entry, with the exception of IL28B, which can be pulled from historical records or performed during screening, and HCV genotype, which can be pulled from historical records up to 6 months before screening or performed at screening. Subjects may be rescreened at the PI's discretion. Laboratory parameters may be repeated as clinically necessary to be resulted within 30 days of Day 0 as required by Johns Hopkins.

Visits during Step 2 must be scheduled on the exact day planned with no visit window. Entry/day 0 and day 7 are to be scheduled 7 days apart. If a participant misses a visit on days 1-6, they will continue on study. Missing a visit does not extend the total duration.

**Table 4: Step 1 and Step 2 Schedule of Events**

Evaluation	Screening	Entry/	Day	Day	Day	Day	Day	Day	Day
	Day -42 – Day -1	Day 0	1	2	3	4	5	6	7
Vital Signs	X	X				X b			X a
Height	X								
Weight	X								
Documentation of HIV status	X								
Documentation of chronic HCV genotype 1a Infection	X								
Documentation of the absence of cirrhosis by Fibroscan	X								
Medical History	X								
Documentation of current medications	X								
Complete Physical Exam	X								
Comprehensive metabolic panel (calculated creatinine clearance )	X								
CBC	X				X b	X a			

Evaluation	Screening Day -42 – Day -1	Entry/ Day 0	Day 1	Day 2	Day 3	Day 4	Day 5	Day 6	Day 7
INR and PTT	X								
Pregnancy Testing	X								
HBsAg	X								
CD4+ (HIV seropositive only)	X								
HIV RNA (HIV seropositive only)	X								
IL28B genotype	X c								
HCV Genotype	X d								
DAA dosing		X	X	X	X	X	X	X	X
Plasma Viral Kinetics (HCV RNA)	X	X	X	X	X	X			X
Stored PBMCs (Immunology)		X				X b			X a
Stored Plasma (Resistance)		X	X	X	X	X			X
Core Needle Biopsy (Liver)		X				X b			X a
Post-Biopsy Clinical Evaluations		X				X b			X a

a Evaluations to be performed at these timepoints for cohort 1 only

b Evaluations to be performed at these timepoints for cohort 2 only

c IL28B result can be pulled from historical records with no time restriction prior to screening or performed at screening if a prior result is unavailable.

d HCV Genotype result can be pulled from historical records within 6 months of screening, or performed at screening if a prior result is unavailable.

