**Total study duration: Up to 30 weeks.**

Table 5: Step 3 and Step 4 Schedule of Events

Evaluation	Step 3 HCV Treatment with SOF/VEL				Step 4 Post-treatment Follow Up	
	Week 2 ± 3 days	Week 4 ± 3 days	Week 8 ± 3 days	Week 12 ± 3 days	Week 16 ± 5 days	Week 24 ± 5 days
Plasma Viral Kinetics (HCV RNA)	X	X	X	X	X	X
Concomitant Medication	X	X	X	X		X
Targeted Physical Exam				X		X
Stored PBMCs (Immunology)		X				X
Stored Plasma (Resistance)	X	X	X	X	X	X

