## 9.0 Adverse events

### 9.1 Non-serious adverse events

The maximum grade of all adverse events will be collected from day 0 through week 4 and documented on the case report form (CRF). At each visit, adverse effects will be ascertained. All inpatient and outpatient clinical assessments and results will be reviewed for the presence of adverse events. All patients will be evaluated by non-directed questioning for the occurrence of adverse events during the course of the study. After noting any *volunteered* adverse events, the question, "Have you had any other problems since I last saw you?" will be asked at each visit. Adverse events will then be explored through directed questioning. Standard guidelines for the management of toxicity will be closely followed to minimize risk to study participants. Adverse events will be graded according to standard clinical trial guidelines.

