## 12.0 Data Safety Monitoring

The study will have external oversight by a Johns Hopkins University Study Monitoring Committee (SMC) comprised of two physicians with extensive training in both HIV and HCV disease. The SMC will conduct its first review when 5 participants have completed Step 2 (paired liver biopsy) and, if deemed necessary by the SMC members, may conduct a second interim review after 10 participants have completed Step 2. The SMC will not oversee the conduct of Step 3 since this reflects treatment with an FDA-approved HCV regimen and the conduct of Step 3 and 4 will be under standard of care procedures.

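### No liver or kidney chemistry is scheduled after the first dose, so laboratory toxicity in Step 2 cannot be systematically detected or graded, although section 9.1 grades all adverse events from Day 0 to Week 4

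*Combined protocol and SAP*

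**What the plan says.** - **Schedule, Steps 1 and 2 (Table 4).** The row "Comprehensive metabolic panel (calculated creatinine clearance" has one mark, in the screening column (Day -42 to Day -1). It has none on Days 0 to 7. The only blood safety test with a mark after dosing begins is the CBC, once per cohort.
- **Schedule, Steps 3 and 4 (Table 5).** The rows are HCV RNA, concomitant medication, targeted physical examination, stored PBMCs and stored plasma.
- **Entry limits (section 5.1, inclusion 9).** "Alanine aminotransferase (ALT) and aspartate aminotransferase level" may be up to 10 times the upper limit of normal. Total bilirubin must be below 3 mg/dL and creatinine clearance at least 30 mL/min.
- **Adverse events (section 9.1).** "The maximum grade of all adverse events will be collected from day 0 through week 4". Among the ways of finding them, "All inpatient and outpatient clinical assessments and results will be reviewed for the presence of adverse events". On severity, "Adverse events will be graded according to standard clinical trial guidelines"; the scale is not named.
- **Repeat tests (section 7.1).** "Laboratory parameters may be repeated as clinically necessary to be resulted within 30 days of Day 0 as required by Johns Hopkins".
- **Oversight (section 12.0).** The Study Monitoring Committee (SMC) first reviews when five participants have completed Step 2. "The SMC will not oversee the conduct of Step 3", and Steps 3 and 4 are placed under standard of care.

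**The concern.** Section 9.1 sets a window (Day 0 to Week 4), a source (results, among others) and an output (the maximum grade of every adverse event). For the liver and kidney, the schedule supplies no result inside that window. A rise in ALT, AST, bilirubin or creatinine without symptoms would be found only if someone ordered a test outside the protocol.

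There is also no Day 0 value. Entry admits people with clearly abnormal liver tests or reduced kidney function. If an unscheduled value came back abnormal, a new event could be told from pre-existing disease only by comparison with a screening value that may be weeks old.

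The gap matters most in Step 2. That step holds the week in which Group A takes the third drug and both biopsies in every participant, and its completion triggers the SMC review. Section 4.2 treats laboratory abnormalities as safety evidence when it reports the placebo comparison for the two-drug regimen. It gives no comparable information for the three-drug regimen. What is at stake is the monitoring of individual participants and the meaning of a safety record with no laboratory liver or kidney events in it.

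**Working it through.** No figure in the plan bears directly on this point. The check is a count of scheduled tests and two short calculations.

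**1. Scheduled metabolic panels per participant**

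| Period | Source | Panels | In the Day 0 to Week 4 window? |
|---|---|---|---|
| Screening | Table 4 | 1 | No |
| Days 0 to 7 (Step 2) | Table 4 | 0 | Yes |
| Weeks 2 and 4 (Step 3) | Table 5 | 0 | Yes |
| Weeks 8 and 12 (Step 3) | Table 5 | 0 | No |
| Weeks 16 and 24 (Step 4) | Table 5 | 0 | No |

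The count is the same for all 15 participants, including the 5 in Group A.

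**2. Could another passage supply the missing values?**

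- Section 12.0 assigns Steps 3 and 4 to standard of care. Routine clinical tests may therefore exist from Day 8 onward, although they are not scheduled study data. Step 2 is not included.
- Section 7.1 permits repeat tests. The sentence sits in the screening section, is permissive, does not name the tests, and is tied to having results within 30 days of Day 0. It may refresh the baseline but does not set up on-treatment monitoring.
- Section 9.1 also uses non-directed and directed questioning. That reaches symptoms, not laboratory values.

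Step 2 therefore has no scheduled source of liver or kidney chemistry.

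**3. Greatest age of the last scheduled value**

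- From the screening window: 42 days at first dose, and 42 + 7 = 49 days at Day 7.
- If the section 7.1 sentence is applied to chemistry: 30 days at first dose, and 30 + 7 = 37 days at Day 7.

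**4. What one scheduled on-treatment panel could show**

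The documents give no event rate, so the true rate p is an assumption, shown over a range. The chance of at least one abnormal result among n people is 1 − (1 − p)^n. After zero events, the one-sided 95% upper bound is 1 − 0.05^(1/n).

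| Assumed p | n = 5 (Group A) | n = 15 (all) |
|---|---|---|
| 1% | 4.9% | 14.0% |
| 5% | 22.6% | 53.7% |
| 10% | 41.0% | 79.4% |
| 20% | 67.2% | 96.5% |
| Upper bound after 0 events | 1 − 0.05^(1/5) = 45% | 1 − 0.05^(1/15) = 18% |

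A panel lets an abnormality in one person be seen and graded. It says little about how often such abnormalities occur.

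**5. Feasibility**

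Plasma for HCV RNA is already drawn on Days 0, 1, 2, 3, 4 and 7 (6 dates) and at Weeks 2 and 4 (2 dates), which gives 6 + 2 = 8 dates inside the window. For scale, two panels each would be 15 × 2 = 30 in total, and three each 15 × 3 = 45.

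**The case against.** **Section 9.1 does not promise chemistry.** It says that whatever results exist will be reviewed, and some do exist: the CBC, vital signs and post-biopsy evaluations. This stands in part. The documents contain a gap between aim and schedule, not a flat contradiction. But a window that claims the maximum grade of all adverse events reads as covering laboratory events, and nothing says that liver and kidney values are left out.

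**Toxicity can still be found.** A reader might infer that liver and kidney toxicity cannot be detected at all. The documents do not support that. Symptomatic events are sought by questioning at every visit, unscheduled tests are not barred, and section 9.1 says standard toxicity-management guidelines will be followed. What is lost is systematic detection from scheduled data.

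**Standard of care covers most of the treatment.** A reader might also count the gap over all 84 treatment days and the follow-up. Table 5 need not list routine clinical tests in steps run under standard of care, so the firm claim is confined to Step 2.

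**Safety is not an objective, and five per group is too few.** Both statements are true. Sections 3.1 to 3.3 list no safety objective, section 11.0 has no safety comparison between groups, and zero events in five leaves an upper bound of 45%. The case for change rests on individual monitoring, which does not depend on group size.

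**The regimens are approved.** Sections 6.1 and 6.2 say so. That lowers the expected risk but does not supply the values that section 9.1 would grade.

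**The table may be damaged.** In the text of Table 4 as read from PDF, the CBC marks fall under Days 3 and 4, where other cohort-specific rows use Days 4 and 7. This looks like a conversion artefact. Nothing suggests that a metabolic-panel mark was lost, but the row should be checked against the PDF.

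**Conclusion.** The point holds for Step 2. With the schedule followed as written, no liver or kidney value is planned after the first dose in any group, and the only planned baseline can be 42 days old at first dose (30 days under the more favourable reading of section 7.1). Laboratory toxicity of those organs therefore cannot be systematically detected or graded from scheduled data in the step that section 12.0 leaves outside standard of care.

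The primary estimate, the change in the proportion of infected hepatocytes, is not affected.

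Two further inferences are tempting but unsupported. One is that the safety comparison of Group A with Group B is spoiled: no such comparison is planned, and five per group could not carry one. The other is that the SMC will necessarily see a falsely clean record: section 12.0 does not describe what the SMC receives, and it may see unscheduled results. The supported statement is weaker. Unless told otherwise, a reader of the safety data could take absence of measurement for absence of toxicity.

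The conclusion assumes that Table 4 is correctly reproduced and that no manual or order set outside these documents adds chemistry in Step 2. It merits a change because the remedy is cheap and concerns participant safety.

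**What to change.** Reconcile Tables 4 and 5 with section 9.1 in one of two ways.

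1. **Preferred.** The sponsor schedules chemistry within the adverse-event window on blood draws that already exist (Days 0 to 4 and 7, Weeks 2 and 4), chooses the timing and number, and adds the results to what the SMC reviews.
2. **Failing that.** State in section 9.1, and tell the SMC, that laboratory liver and kidney toxicity is not systematically assessed, so that an absence of such events is not read as evidence of safety.

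In either case, say whether the repeat-laboratory sentence in section 7.1 applies to chemistry.

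The first option costs a few dozen routine panels (30 to 45 at two or three per participant), with no new visit or venepuncture, and means more graded laboratory events to record. The second costs a sentence or two.

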### **7.3 Step 3. HCV treatment with SOF/VEL**

The remaining 11 weeks of DAA therapy represents standard of care treatment for HCV.

Following the completion of Step 3, all participants will be given treatment with sofosbuvir/velpatasvir fixed-dose combination tablet from treatment day 8 to day 84 (total treatment duration of Step 2 plus Step 3 is 84 days or 12 weeks). Plasma HCV RNA levels will be obtained as per Table 5. Visits must occur within the windows indicated on the schedule of events.

